## **10 STUDY PROCEDURES AND ASSESSMENTS**

Study assessments will be obtained prior to cataract surgery with the UNITY VCS and postoperatively at the study visits outlined below:

- Screening – Visit 0 (Day -60 to 0 prior to treatment)
- Surgery – Visit 00 (Day 0)
- 1 Day – Visit 1 (Day 1 to 3)
- 1 Week – Visit 2 (Day 4 to 10)
- 1 Month/Exit – Visit 3 (Day 28 to 42)

In addition to the scheduled visits listed above, the following visit may apply as needed:

- Unscheduled Visit (completed when a treated subject reports for additional follow-up)

Clinical assessments to be obtained at study visits are outlined in [Table 3–1](#) Schedule of Study Procedures and Assessments and are defined in the sections below.

## 10.1 Informed Consent and Screening

The investigator or delegate must explain the purpose and nature of the study, and have the subject read, sign, and date the IRB/IEC-approved informed consent document. The subject must sign the ICF BEFORE any study-specific procedures or assessments can be performed, including study-specific screening procedures. Additionally, have the individual obtaining consent from the subject and a witness, if applicable, sign and date the informed consent document.

The investigator or delegate must provide a copy of the signed document to the subject and place the original signed document in the subject's chart, or provide documentation as required by local regulations.

If a patient has reported for routine cataract screening, then data obtained from the routine evaluation can be used for screening data as long as protocol requirements for timeframe (within 60 days of surgery) and required details have been met. Routine cataract screening data include, but are not limited to slit lamp exam, IOP, dilated pupil size, keratometry, biometry (ACD, AL), Snellen BCDVA with manifest refraction, and dilated fundus exam.

## 10.2 Description of Study Procedures and Assessments

Study-specific procedures and assessments described here may include SOC; other SOC procedures performed in the clinical management of the subject are not excluded.

Detailed descriptions of assessments and procedures are provided in the MOP. The investigator is responsible for ensuring that all procedures and assessments are delegated to appropriately qualified site personnel.

### 10.2.1 Demographics

Obtain demographic information including age, race, ethnicity, and sex.

### 10.2.2 Medical and Ocular History

Collect medical history information, including information on all medications used within the past 30 days of signing the informed consent form. Include herbal therapies, vitamins, and all over-the-counter as well as prescription medications. Throughout the subject's participation,

obtain information on any changes in medical health and/or the use of concomitant medications.

Medical History and Concomitant Medications will be collected in the eCRF as outlined in the MOP.

### **10.2.3 Adverse Event Collection: Safety Assessment**

Assess and record any adverse events that are observed or reported since the previous visit, including those associated with changes in concomitant medication dosing.

Note: AEs and device deficiencies must be recorded for all enrolled subjects from the time of signature of informed consent, regardless of subject enrollment status (screen failure).

### **10.2.4 Slit Lamp Biomicroscopy: Safety Assessment**

SLE of the cornea, iris/anterior chamber, and lens must be performed before instillation of any diagnostic eye drops at the screening visit.

Refer to the MOP for grading scales for study specific assessments.

### **10.2.5 Device Deficiencies: Safety Assessment**

Assess and record any device deficiencies that are reported or observed since the previous visit. Requirements for reporting device deficiencies in the study can be found in Section 11.

Note: AEs and device deficiencies must be recorded for all enrolled subjects from the time of signature of informed consent, regardless of subject enrollment status (screen failure).

### **10.2.6 Dilated Fundus: Safety Assessment**

Dilated fundus examination includes ophthalmoscopic assessments of the vitreous, retina, macula, choroid, and optic nerve.

### **10.2.7 Uncorrected Distance Visual Acuity: Safety Assessment**

Snellen visual acuity testing without manifest refraction must be performed prior to any assessment requiring administration of eye drops to dilate the eye, or any assessment requiring contact with the eye.

## **10.2.8 Best Corrected Distance Visual Acuity: Safety Assessment**

Snellen visual acuity testing with manifest refraction must be performed prior to any assessment requiring administration of eye drops to dilate the eye, or any assessment requiring contact with the eye.

## **10.2.9 Intraocular Pressure: Safety Assessment**

Intraocular pressure must be measured using SOC.

## **10.2.10 Urine Pregnancy Test: Other Assessment**

A urine pregnancy test is required for female subjects of childbearing potential that are not postmenopausal or surgically sterile.

## **10.2.11 Keratometry: Eligibility Assessment**

Capture keratometry measurements of the central cornea using SOC.

## **10.2.12 Pupil Size: Eligibility Assessment**

Measure dilated pupil size under photopic condition using SOC.

## **10.2.13 Biometry: Eligibility Assessment**

[figure not shown]
Perform biometry using SOC. Document the following: ACD, AL.

## **10.2.14 Assessment through the operating microscope: Other Assessment**

If femtosecond laser is used then perform an assessment of the cornea and conjunctiva, and other femtosecond laser related findings through the operating microscope after femtosecond laser-assisted incision and/or capsulotomy but before entry into the eye for cataract removal surgery.

## **10.2.15 Time from incision entry to incision closure: Secondary Performance Assessment**

Obtain time from incision entry into the eye to incision closure using a stopwatch.

### **10.3 Unscheduled Visits**

An Unscheduled Visit (USV) is defined as follows:

- Ocular examination that is not SOC and not required by the protocol
- Examination conducted by the study staff
- New findings, or change to a previous finding was discovered

A USV may or may not result in the capture of an adverse event. Likewise, an adverse event may be captured without the report of a USV (e.g., AE identified subsequent to study eye examination by nonstudy personnel).

If a subject visit occurs between any regularly scheduled visit and the visit is conducted by study personnel, this visit must be documented as an USV. If the subject seeks medical attention outside the clinic (for example, at an Emergency Room) or at the clinic but is seen by nonstudy personnel, the investigator is to capture adverse event-related information on the adverse event form upon becoming aware.

During all USVs, the investigator must conduct the following procedures:

- Collect adverse event information, if applicable
- Collect device deficiency information, if applicable
- Collect SSI information, if applicable
- Record changes in medical condition or concomitant medication

The investigator may perform additional procedures for proper diagnosis and treatment of the subject. These include but are not limited to those noted in [Table 3–1](#) Schedule of Study Procedures and Assessments. The investigator must document this information in the subject's case history source documents.

If during a USV the subject is discontinuing from the study, the investigator must conduct Exit procedures according to [Table 3–1](#) Schedule of Study Procedures and Assessments and Section [10.4.3](#), as possible.

## **10.4 Discontinued Subjects**

### **10.4.1 Screen Failures**

Subjects who were excluded from the study after signing the informed consent and prior to exposure.

The investigator must document the reason for the screen failure in the subject's case history source documents.

Subject numbers must not be re-used.

### **10.4.2 Discontinuations**

Discontinued subjects are individuals who voluntarily withdraw or are withdrawn from the study by the investigator after signing informed consent, meeting eligibility criteria, and are exposed to IP.

Subject numbers of discontinued subjects must not be re-used (i.e., subject replacement is not allowed).

Subjects may discontinue from study or study treatment at any time for any reason. Subjects may also be discontinued from study treatment at any time if, in the opinion of the investigator, continued treatment poses a risk to their health.

For subjects choosing to discontinue from the study after exposure to IP, the investigator must complete all Exit procedures according to [Table 3–1](#) Schedule of Study Procedures and

Assessments, if the subject is willing and able, and if in the opinion of the investigator it is safe for the subject to do so.

The investigator must document the reason for study or treatment discontinuation in the subject's case history source documents.

To ensure the safety of all subjects who discontinue early, investigators must assess each subject and, if necessary, advise them of any therapies and/or medical procedures that may be needed to maintain their health.

#### **10.4.3 Schedule of Procedures and Assessments for Subjects Discontinued from Investigational Product**

If a subject discontinues from study treatment, every effort must be made to keep the subject in the study and to continue with the study assessments as specified in the schedule of study procedures and assessments until the final visit.

### **10.5 Clinical Study Termination**

The study sponsor reserves the right to suspend or close the investigational site or suspend or terminate the study in its entirety at any time.

If the clinical study is prematurely terminated or suspended by the study sponsor:

- The study sponsor must:
  - Immediately notify the investigator(s) and subsequently provide instructions for study termination.
  - Inform the investigator and the regulatory authorities of the termination/suspension and the reason(s) for the termination/suspension.
- The investigator must:
  - Promptly notify the IRB/IEC of the termination or suspension and of the reasons.
  - Provide subjects with recommendations for poststudy treatment options as needed.

The investigator may terminate the site's participation in the study for reasonable cause.

#### **10.5.1 Follow-up of subjects after study participation has ended**

[figure not shown]
Following this study, the subject will return to their eye care professional for their routine eye care.

## 11 ADVERSE EVENTS AND DEVICE DEFICIENCIES

### 11.1 General Information

An AE is any untoward medical occurrence, unintended disease or injury, or untoward clinical signs (including abnormal laboratory findings) in subjects, users, or other persons, whether or not related to the investigational medical device (test product). Refer to the Glossary of Terms and figures below for categories of AEs and SAEs.

**Figure 11-1** Categorization of All Adverse Events

\*In this study, only AEs related to the investigational product/device (i.e., UNITY VCS) are considered as device related ADE.

## **Specific Events Relevant to this Protocol**

In addition to reporting all AEs (serious and nonserious) meeting the definitions, the investigator must report any occurrence of the following as an SAE including but not limited to:

### ***Serious Adverse Events***

- Postoperative corneal incision site wound leakage
- Hypopyon
- Hyphema
- Toxic anterior segment syndrome
- Posterior capsular tear
- Vitreous prolapse
- Iridodialysis
- Posterior lens dislocation
- Chronic corneal edema (corneal stromal or epithelial swelling resulting in BCDVA of  $\leq 20/40$  at  $\geq 1$  month)
- Clinically significant cystoid macular edema
- Uncontrolled increase in IOP  $\geq 10$  mmHg over baseline and at least 25 mmHg
- Endophthalmitis
- Retinal detachment
- Pupillary block
- Suprachoroidal hemorrhage
- Vitreous hemorrhage
- Vision-threatening surgical problems
- Secondary surgical intervention (excluding posterior capsulotomy)

[figure not shown]
NOTE: Wound burps during the first week postoperatively, suture removal, planned blepharoplasty, and Nd:YAG capsulotomy (for PCO) are not considered adverse events for this study.

Any other potentially sight-threatening event may also be considered serious based on the judgment of the investigator and should be reported appropriately as delineated in Section [11.3](#).

AEs occurring in association with a device that is used in conjunction with the UNITY VCS (e.g., femtosecond laser) will be classified separately from those associated with the investigational device itself.

### ***Device Deficiencies***

A device deficiency may or may not be associated with subject harm (i.e., ADE or SADE); however, not all ADEs or SADEs are due to a device deficiency. The investigator should determine the applicable category for the identified or suspect device deficiency and report any patient harm separately. [REDACTED]

## **11.2 Monitoring for Adverse Events**

At each visit, after the subject has had the opportunity to spontaneously mention any problems, the investigator should inquire about AEs by asking the standard questions shown below and report as applicable:

- “Have you had any health problems since your last study visit?”
- “Have there been any changes in the medicines you take because of a new health issue since your last study visit?”

In addition, changes in *any protocol-specific parameters and/or questionnaires* evaluated during the study are to be reviewed by the investigator. Any untoward (unfavorable and unintended) change in *a protocol-specific parameter or questionnaire response* that is clinically relevant, in the opinion of the investigator, is to be reported as an AE. These clinically relevant changes will be reported regardless of causality.

### 11.3 Procedures for Recording and Reporting

AEs are collected from the time of informed consent. Any pre-existing medical conditions or signs/symptoms present in a subject prior to the start of the study (i.e., before informed consent is signed) are not considered AEs in the study and should be recorded in the Medical History section of the eCRF.

In addition, aqueous cells and flare, corneal edema, eye redness, raised IOP, subconjunctival hemorrhage, and superficial punctate keratitis are examples of early postoperative findings that are typically observed following ocular surgery. These are not considered AEs if they can be reasonably expected to resolve within 2 weeks and not result in any untoward long term visual outcome impact. Expected complications from use of femtosecond laser-assisted procedures as noted in Section 5.3 will not be considered device related AEs..

For each recorded event, the ADEs and SAEs documentation must include: date of occurrence, severity, treatment (if applicable), outcome, and assessments of the seriousness and causality. In addition, the investigator must document all device deficiencies reported or observed with the test product on the Device Deficiency eCRF. The site must submit all available information on ADEs, SAEs, and device deficiencies to the Study Sponsor immediately as follows:

- ADEs or SAEs are documented on the *Serious Adverse Event and Adverse Device Effect* eCRF within 24 hours of the investigator's or site's awareness.
- Device deficiencies are documented on the *Device Deficiency* eCRF within 24 hours of the investigator's or site's awareness.
- Additional relevant information after initial reporting must be entered into the eCRF as soon as the data become available.
- Document any changes to concomitant medications on the appropriate eCRFs.
- Document all relevant information from Discharge Summary, Autopsy Report, Certificate of Death etc., if applicable, in the narrative section of the *Serious Adverse Event and Adverse Device Effect* eCRF.

*Note:* Should the EDC system become nonoperational, the site must complete the appropriate paper *Serious Adverse Event and Adverse Device Effect* and/or *Device Deficiency* Form. The completed form is emailed to the Study Sponsor at [[contact]](mailto:[contact]) for USA-based sites and at [[contact]](mailto:[contact]) for AUS-based sites, according to the

timelines outlined above; however, the reported information must be entered into the EDC system once it becomes operational.

In addition to recording all AEs into the EDC system, any AEs and device deficiencies for nonstudy marketed devices/products (e.g., Alcon's or other manufacturers' products used concomitantly during the study will be considered and processed as spontaneous following the postmarket vigilance procedures) and should be communicated to the device's/product's manufacturer as per local requirements.

**Study sponsor representatives may be contacted for any protocol related question and their contact information is provided in the Manual of Procedures that accompanies this protocol.**

Further, depending upon the nature of the AE or device deficiency being reported, the Study Sponsor may request copies of applicable portions of the subject's medical records. The investigator must also report all AEs and device deficiencies that could have led to a SADE according to the requirements of regulatory authorities or the IRB/IEC.

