## 5.3 Risks and Benefits

The benefit of cataract surgery is the removal of the opacified, cloudy crystalline lens. In comparison with predecessor phacoemulsification systems, the UNITY VCS anterior segment functionality provides enhancements that are designed to benefit patients. The two most used enhancements of UNITY VCS during cataract surgery will relate to fluidics and ultrasound. The fluidics enhancement was designed with the intent to allow surgeons to operate at lower IOP and higher vacuum while maintaining anterior chamber stability. In specific, operating at lower, more physiological IOP may be associated with greater reported patient comfort during surgery (Hou 2012), improved visual recovery due to better preservation of corneal endothelial health, and less macular edema postoperatively (Suzuki 2009, Chen 2012) as well as reduced complications due to less impact on retinal blood flow/reduction of ischemia (Findl 1997, Takhtaev 2019). The ultrasound enhancement was

designed to improve crystalline lens cutting efficiency and reduce energy. The overall potential benefit would be a safer and more efficient procedure.

Risk management principles have been applied to both the planning and the intended conduct of the clinical investigation, to ensure the reliability of the clinical data generated and the safety of the subjects.

The clinical investigation risks are managed through appropriate training and monitoring according to the protocol-specific monitoring plan. [REDACTED]

Participation in the clinical study will require the subject to undergo cataract surgery and implantation of a hydrophobic acrylic intraocular lens into the capsular bag. The use of femtosecond laser-assisted incisions and capsulotomies per product label is optional at the discretion of patient and surgeon; use of femtosecond laser-assisted procedures is not required for this study.

Complications may occur on the surgery day or throughout the postoperative period. As with any type of intraocular surgery, there is a possibility of complications due to anesthesia, drug reactions, and/or surgical problems. The surgical procedure can exacerbate a pre-existing ocular condition. [REDACTED]

[REDACTED]  
[REDACTED]  
[REDACTED]  
[REDACTED].

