#### ***Intensity (Severity)***

Mild            An AE is mild if the subject is aware of but can easily tolerate the sign or symptom.

Moderate      An AE is moderate if the sign or symptom results in discomfort significant enough to cause interference with the subject's usual activities.

Severe          An AE is severe if the sign or symptom is incapacitating and results in the subject's inability to work or engage in their usual activities.

For every AE in the study, the Investigator must assess the causality (Related or Not Related to the medical device or study procedure). An assessment of causality will also be performed by Study Sponsor utilizing the same definitions, as shown below:

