#### ***Causality***

Related	An AE classified as related may be either definitely related or possibly related where a direct cause and effect relationship with the medical device or study procedure has not been demonstrated, but there is a reasonable possibility that the AE was caused by the medical device or study procedure.
Not Related	An AE classified as not related may either be definitely unrelated or simply unlikely to be related (i.e., there are other more likely causes for the AE).

The Study Sponsor will assess the AEs and may upgrade the investigator's assessment of seriousness and/or causality. The Study Sponsor will notify the investigator of any AEs that are upgraded from nonserious to serious or from unrelated to related.

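### Protocol 11.3 rules expected femtosecond-laser complications not device related without exception, which conflicts with its own causality definition for events to which UNITY VCS may also have contributed

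*Protocol*

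**What the plan says.** Protocol 5.3 permits the laser as an adjunct: "The use of femtosecond laser-assisted incisions and capsulotomies per product label is optional at the discretion of patient and surgeon". Laser fragmentation is an exclusion criterion (8.2), so laser use is confined to incisions and capsulotomies. No share of laser-assisted eyes is planned or capped.

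Four parts of the protocol bear on attribution:

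- **11.1, note to Figure 11-1:** "only AEs related to the investigational product/device (i.e., UNITY VCS) are considered as device related ADE".
- **11.1, Serious Adverse Events:** "AEs occurring in association with a device that is used in conjunction with the UNITY VCS (e.g., femtosecond laser) will be classified separately" from those of the investigational device.
- **11.3, recording rules:** "Expected complications from use of femtosecond laser-assisted procedures as noted in Section 5.3 will not be considered device related AEs".
- **11.3, Causality:** investigator and sponsor each assess every AE. Related includes events where "there is a reasonable possibility that the AE was caused by the medical device or study procedure". The sponsor "may upgrade the investigator's assessment of seriousness and/or causality".

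If the laser is used, Protocol 10.2.14 requires the cornea, conjunctiva and other laser-related findings to be examined "after femtosecond laser-assisted incision and/or capsulotomy but before entry into the eye for cataract removal surgery".

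SAP 5.3.1 provides counts, percentages and listings of all AEs. It specifies no split by relationship to the device or by laser use.

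**The concern.** The recording rule in 11.3 settles relatedness in advance for a predefined group of complications. The sentence just before it, on early postoperative findings, carries conditions (expected resolution within 2 weeks, no lasting visual effect). The laser sentence carries none, and in particular has no clause for an event that UNITY VCS may have helped to cause or may have worsened.

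The study's stated purpose is device-specific safety data, and there is no comparator arm. Whether an individual event counts against UNITY VCS therefore rests on the causality rating. That rating decides whether an event is an ADE, whether a serious event is a SADE, and whether a non-serious event goes to the sponsor within 24 hours. If two rules in one section give different ratings for the same event, sites may classify like events differently, and the error would favour the device.

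**Working it through.** The documents state no device-related AE rate, laser share or rate of listed complications, so there is no figure to reproduce. The check is mainly a comparison of the rules.

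**1. Apply both rules to an expected-type complication in a laser-assisted eye.**

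| Plausible cause | Laser sentence in 11.3 | Causality definition in 11.3, with 11.1 | Same answer? |
|---|---|---|---|
| Laser only | Not device related | Not related to UNITY | Yes |
| UNITY only | Outside the sentence if read causally; inside it if read as a list of event types | Related to UNITY | Depends on the reading |
| Laser and UNITY both | Not device related | Related, since a reasonable possibility is enough | No |

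The causality definition covers the device or the study procedure, so a Related rating alone does not make an event device related. The conflict is limited to events where the reasonable possibility concerns UNITY VCS itself. For the third row it remains even on a causal reading, because a complication of laser use can also have been worsened during lens removal.

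**2. Look for a tie-breaker.** The separation rule in 11.1 does not cover events that either device could have caused. The sponsor's power to upgrade is discretionary and does not set aside the laser sentence. Nothing in 10.2.14 or 11.3 links the pre-entry findings to attribution.

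**3. Is overlap plausible?** The laser complications that 11.3 refers to are not identifiable in the visible text of 5.3, part of which is blacked out; that is not a fault in the plan. Section 5.3 does say that the complications described before that statement have been reported with phacoemulsification. Overlap is therefore plausible, but which events overlap cannot be checked.

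**4. What changes for an affected event?**

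- It stays an AE and stays in the overall SAP tables and listings.
- If serious, it is still reported within 24 hours as an SAE, but not categorised as a SADE.
- If non-serious, it is no longer an ADE and loses the 24-hour route.

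**5. Scale, by assumption only.** Let r be the true rate of UNITY-related events of the listed types (the same in laser and manual eyes), f the share of laser-assisted eyes, and s the share of such events in laser-assisted eyes that the sentence reclassifies. The recorded rate is r × (1 − f × s).

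- With s = 0 (causal reading, no shared-cause events), it equals r and the loss is zero.
- With s = 1 (worst case), it equals r × (1 − f):

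| r (assumed) | f = 10% | f = 25% | f = 50% | f = 100% |
|---|---|---|---|---|
| 2% | 1.8% | 1.5% | 1.0% | 0% |
| 5% | 4.5% | 3.75% | 2.5% | 0% |

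For example, 2% × (1 − 0.50) = 1.0%. In 100 eyes that is 1 event recorded instead of 2, and the exact (Clopper-Pearson) 95% interval moves from 0.24–7.04% to 0.03–5.45%. The SAP plans no such interval; it is shown only for scale.

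**The case against.** The strongest reply is that the laser sentence is itself causal: it concerns complications arising from laser use, not every event of a given type in a laser-assisted eye. An event caused by UNITY VCS alone is not a laser complication. Sections 11.1 and 11.3 keep attribution case by case, and the sponsor can correct a wrong rating upward. On this view the sentence only restates the separation of devices in 11.1.

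Much of this stands. A reader might infer that the protocol classifies by event type, so that every UNITY-caused event of a listed type in a laser-assisted eye falls out of a device-related rate, which is then biased downward. The documents do not support that. Type-based classification is one reading, not what the text declares; the list cannot be seen; and the SAP defines no device-related rate for events to fall out of.

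The effect on 24-hour reporting is also limited. Posterior capsular tear, postoperative incision leakage and chronic corneal edema are on the 11.1 list of events always reported as SAEs, so they reach the sponsor within 24 hours whatever the causality. Early corneal edema reasonably expected to resolve within 2 weeks, with no lasting visual effect, is not an AE in any eye.

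The reply does not dispose of the shared-cause event. If the sentence only restated 11.1 it would add almost nothing; what it does add is an outcome fixed in advance, and for shared-cause events that outcome contradicts the causality definition.

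**Conclusion.** The point holds as an unresolved conflict between two rules in Protocol 11.3, limited to expected laser complications to which UNITY VCS may also have contributed. Some of these events could lose ADE or SADE classification, and the non-serious ones the 24-hour ADE route. They would not disappear from the overall AE counts and listings.

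The size cannot be determined from the documents. It runs from zero (strictly causal reading, no shared-cause events) to all UNITY-related events of the listed types in laser-assisted eyes (worst case of the list reading). The worked rates rest on an assumed laser share, an assumed event rate and equal rates in laser and manual eyes, so they are not evidence of bias. Because the SAP specifies no breakdown by relationship or laser use, its planned summary tables would not show whether the conflict had any effect. The change is worth making because it is small and protects the classification that a device-specific safety study depends on.

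**What to change.** Replace the laser sentence in Protocol 11.3 with wording such as:

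> An expected complication of a femtosecond laser-assisted procedure is classed as not device related only if individual assessment under the causality definition in this section, informed by the pre-entry microscope findings (Section 10.2.14), finds no reasonable possibility that UNITY VCS caused or worsened it.

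The pre-entry findings should inform the judgement, not decide it. A rule allowing a laser-only classification only for events documented before entry would misclassify laser-caused events that first appear later.

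In SAP 5.3.1, add a tabulation of AEs by relationship to UNITY VCS and by laser use (yes or no).

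The cost is one protocol sentence, with the approvals that Protocol Section 4 requires for an amendment, and one additional SAP table. No new examination is needed: 10.2.14 is already required in laser-assisted eyes and so should identify them. The downside is that a few laser-caused events may be rated possibly UNITY related, so the count of device-related events may be slightly less favourable.
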